#### Inclusion Criteria:

Inclusion criteria include 1) Age 50+; 2) significant worry as shown by a score of 50 or greater on the Penn State Worry Questionnaire (PSWQ); 3) must be English speaking; 4) must have a health care provider and provide written authorization to research team to communicate with this individual and any referring community agency provider; 5) must have access to a telephone, and 6) live, work, worship attend community functions, and/or receive health care in target geographic areas.

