## F2. Procedure

Recruitment will be conducted via community outreach activities and referrals from partner social service and faith-based organizations. During community outreach events, information about the study will be provided in the form of verbal educational presentations or written project descriptions in brochures, community organization and church newsletters, or bulletins (Attached in Section S - Please see Calmer\_Life\_Flyer.pptx and Calmer Life Bulletin.docx). Potential participants will provide contact information to be called by the study staff or they will contact study staff directly. In order for potential participants to express interest and provide their contact information confidentially at public events, staff will distribute handouts that will include the two approved telephone anxiety screening questions (GAD-2) to allow participants to decide if the Calmer Life study would be appropriate for them (see Section S, "Calmer\_Life\_Interest Form.docx"). Any responses to these screening questions will not be used as study data, but will rather serve as informational tools to assist potential participants in deciding if the Calmer Life study may be appropriate for them. These potential participants will be asked two anxiety screening questions (GAD-2) on the phone as an initial screener, but participant responses will not be used as data. Responses will be used only to determine who will be invited to an in-person consent appointment.

All individuals who express interest in participation and respond affirmatively to one of the two screening questions will be scheduled for an in-person visit in a community setting or the participant's home, based on participant preference, to review the consent form, conduct a more formal screening, and obtain demographic information. Participants who provide written consent will complete a demographic information form, two anxiety screening measures (GAD-2), a six-item cognitive screener, the PSWQ and the PHQ-9. This will take

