Excluded participants will receive a list of community resources. Participants who meet all inclusion criteria will complete a baseline telephone assessment. During baseline, the following measures will be administered via telephone: A separate VA release form will be used to communicate with the patient's health care provider (s) and any referring community agency provider if at any time the participant needs immediate treatment (ie, for suicidal intent, psychotic symptoms). Penn State Worry Questionnaire (PSWQ), Geriatric Anxiety Inventory (GAI-SF), Generalized Anxiety Disorder 7 (GAD-7), Patient Health Questionnaire (PHQ-9), Geriatric Depression Scale (GDS), Late-life Functional Disability Index (LL-FDI), Health-related Quality of Life (SF-12), Insomnia Severity Index (ISI), Service Use Questionnaire, and Utilization of Medications, PTSD Checklist for DSM-5 (PCL-5) and the Brief RCOPE. Upon completion of baseline assessment, participants will be assigned randomly to CL or ECC and will follow 6 months of procedures as described in Section F1. Assessments at 6 and 9 months will repeat the baseline measures, except for the Brief RCOPE, with the addition of the Client Satisfaction Questionnaire (CSQ). Participants who complete the CL intervention and are classified as low or high performers (maximum of 30 total) will be selected to complete qualitative interviews following completion of all outcome assessments. All assessments, qualitative interviews and intervention sessions will be recorded using the Olympus DS-5000id or DS-7000. Co-investigators will serve as supervisors to review integrity of randomly selected diagnostic and outcome assessments. Recordings from the CL and ECC sessions will be randomly selected for treatment integrity review by MEDVAMC psychologists on the research team who have expertise in the identification and treatment of late-life anxiety.

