Specific Aim 1. Examine the comparative effectiveness of CL and ECC in older adults with clinically significant worry on primary outcomes (worry, GAD-related symptoms). Primary outcome analyses at 6 months will be intention-to-treat (ITT) and will use the multiple imputation procedures PROC MI and MINANALYZE in SAS Version 9.3 to estimate missing observations. Another set of analyses will be for completers and will include only observed data. We will first employ Analysis of Covariance (ANCOVA) to examine treatment differences in worry and anxiety at 6 months (post intervention). We will conduct separate models for worry and anxiety. All models will include treatment group (ie, CL versus ECC) as a predictor and respective baseline scores and any demographic or clinical variables that differed between treatment groups at baseline as covariates. Treatment effect sizes will be calculated. We will calculate intraclass correlation coefficients (ICC) for both primary outcomes to determine the degree of clustering within referral source (social service or faith-based setting). If a substantial proportion of variability in either outcome is accounted for by referral source (ie, ICC greater than 0.10), multilevel models will be employed using SAS PROC MIXED to minimize the bias of error terms that may occur from dependency due to nesting effects. These models will include the intercept as a random effect and treatment group, respective baseline scores, and variables that differed between treatment groups at baseline as fixed effects.

Specific Aim 2. Examine the comparative effectiveness of CL and ECC on secondary outcomes (anxiety, depression, sleep, functional status, quality of life, service use). Analyses will be conducted as in Aim 1, first using ITT and multiple imputation to estimate missing data. Another set of analyses will be conducted for study completers. We will use ANCOVA to examine treatment differences at 6 months in secondary outcomes (anxiety, depression, sleep, functional status, quality of life, service use), using separate models for each measure. Effect sizes will be calculated. As in Aim 1, these models will include the intercept as a random effect and treatment group, baseline scores, and variables that differed between treatment groups at baseline

as fixed effects.

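### The worry model uses one of two pre-randomisation PSWQ readings; adding the screening score is a small, free gain in precision, not the repair of a bias

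*Combined protocol and SAP*

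**What the plan says.** F2 (Procedure) describes two separate contacts before randomisation. At the in-person visit, people who consent complete a demographic form and "two anxiety screening measures (GAD-2), a six-item cognitive screener, the PSWQ and the PHQ-9". Entry requires a PSWQ of 50 or more (Inclusion Criteria; F2) and a PHQ-9 below 20 (Exclusion Criteria; F2). After that, "Participants who meet all inclusion criteria will complete a baseline telephone assessment", and the telephone battery begins with "Penn State Worry Questionnaire (PSWQ), Geriatric Anxiety Inventory (GAI-SF), Generalized Anxiety Disorder 7 (GAD-7), Patient Health Questionnaire (PHQ-9" and continues with further scales. Allocation comes next: "Upon completion of baseline assessment, participants will be assigned randomly to CL or ECC".

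G2, Specific Aim 1, analyses worry and anxiety at 6 months in separate ANCOVA models. On covariates it says "All models will include treatment group (ie, CL versus ECC) as a predictor and respective baseline scores", plus demographic or clinical variables found to differ between the arms at baseline; the opening of G2 sets p < 0.25 for bringing such variables in. Specific Aim 3 repeats the analyses at 9 months. Missing outcomes are imputed with PROC MI, but the imputation variables are not listed.

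J2 (Consent Procedures) also describes screening. It leaves out the PHQ-9 and calls the worry scale PSWQ in one sentence and PSWQ-A in the next.

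**The concern.** Every randomised participant should have two PSWQ scores that treatment cannot have affected. Since F2 lists the PSWQ among the measures given at baseline, the baseline score in G2 is, on a plain reading, the telephone one. G2 does not define the term, and no section makes the screening score a planned covariate, part of an average, or a named imputation predictor.

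One questionnaire score is a noisy reading of a person's usual worry. A second reading normally carries some further information about the 6-month score, so leaving it out makes the residual variance of the worry comparison a little larger than it need be. The same applies to the PHQ-9 as a depression outcome. At stake is precision in a trial planned around 128 analysable people. G1 cites prior primary-outcome effects of 0.40 to 0.50 and powers the trial at the top of that range.

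**Working it through.** **1. The plan's own figure.** G1 gives d = 0.50, two-sided alpha 0.05, 80% power, 64 per group and 15% attrition. The two-sample t calculation gives 63.8 per group, rounded up to 64, with power 0.801. Attrition: 128/0.85 = 150.6, against 150 stated. Both reproduce. The calculation takes no credit for baseline adjustment, so it does not depend on this point.

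**2. Formula for the gain.** Let b be the correlation of the telephone PSWQ with the 6-month PSWQ, s that of the screening PSWQ with the 6-month PSWQ, and q that between the two readings. Before allowing for the cut at 50, adding the screening score to a model that already holds the telephone score lowers residual variance by the fraction

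(s - q·b)² / [(1 - q²)(1 - b²)].

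None of the three correlations is in the documents; all are assumptions.

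| b | s | q | Calculation | Reduction |
|---|---|---|---|---|
| 0.5 | 0.5 | 0.8 | 0.0100 / (0.36 × 0.75) | 3.7% |
| 0.6 | 0.6 | 0.7 | 0.0324 / (0.51 × 0.64) | 9.9% |
| 0.6 | 0.5 | 0.8 | 0.0004 / (0.36 × 0.64) | 0.2% |

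The third row shows what drives the result. When s is close to q·b, the screening score says almost nothing that the telephone score has not already said.

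**3. Allowing for the cut at 50.** Selection narrows the screening score and weakens it as a predictor. A trivariate-normal simulation truncated at screening PSWQ of 50 or more used these assumptions: pre-screen mean 50-60, SD 11, q = 0.7-0.9, b and s = 0.5-0.6.

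- Equal correlations (b = s): the residual variance ratio is about 0.92 to 0.99, a reduction of about 1-8%. Equivalent participants are 128 × (1/ratio - 1). At the ends, 128 × (1/0.987 - 1) = 1.7 and 128 × (1/0.924 - 1) = 10.5, so about 2 to 11.
- Screening weaker (s = 0.5, b = 0.6): the reduction is about 0.1% at q = 0.8, below 0.1% at q = 0.85, and about 1-1.5% at q = 0.7 or 0.9. At q = 0.8 to 0.85 this is 0 to 0.2 participants.

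**4. Effect on power.** Power = Φ(d / √(2v/n) - 1.96), with n = 64 per group and v the residual variance as a share of the outcome variance. With half of those screened passing the cut, b = s = 0.6 and q = 0.7, v falls from 0.791 to 0.748 (0.748/0.791 = 0.946, a 5.4% reduction). Power at d = 0.50 moves from 88.9% to 90.5%. Across the truncated scenarios with equal correlations of 0.5-0.7 and 50% or 70% passing, the rise is about 0.4 to 2.2 points; with screening weaker it is close to nil. At d = 0.40, untruncated, b = s = 0.5 and q = 0.8, power moves from 74.3% to 75.9%.

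**The case against.** The strongest reply is that ANCOVA on one baseline score is standard and valid, and that this plan has room to spare. Under the assumptions above, the single-baseline model already gives roughly 85-92% power at d = 0.50, against the 80% that G1 claims. Adding the screening score brings 0 to about 2 points. The size also depends on correlations that nobody has supplied. Screening is the earlier reading, is taken in person and is truncated, so it may well be the weaker predictor. All of this stands, and it is why the change is optional.

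It is also fair to say that G2 does not forbid using the screening score. The score could enter through the p < 0.25 rule, and since the imputation variables are unlisted, its absence from PROC MI is not shown. That stands too, but the p < 0.25 rule admits a variable because of chance imbalance, which is no substitute for pre-specifying a prognostic covariate.

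Three stronger readings are tempting, and the documents do not support them.

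- A reader might infer that screening supplies the only worry score held for everyone. F2 randomises only after the baseline assessment is complete, and that assessment includes the PSWQ, so both readings should exist for every randomised participant. Screening helps imputation only as an additional predictor.
- A reader might infer that selecting at 50 biases the comparison through regression to the mean. That affects both randomised arms alike, and adjusting for a separate reading taken after selection is a sound way to handle it. In the simulations 6-25% of randomised people fall below 50 at the telephone reading. This shows that the two readings differ; it is not a defect of the plan.
- A reader might infer a gain for both primary outcomes. For GAD-related symptoms, screening collects only the GAD-2.

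**Conclusion.** The point holds as missed efficiency in the worry model. It is not an error or a source of bias, and the stated sample size and power stand. The gain is a reduction in residual variance of about 1-8% if the two readings predict the 6-month score equally well, and close to 0% if screening is the weaker predictor: about 0 to 11 participants on 128. This rests on the assumed correlations, SD and pre-screen mean, and on the same instrument being used on both occasions, which the PSWQ and PSWQ-A wording in J2 leaves uncertain. That the screening score adds prognostic information is reasonable but not shown in the documents. The gain for the PHQ-9 was not calculated. Separately from the size of the gain, G2 should say which PSWQ reading is the baseline score, because two exist.

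**What to change.** Optional, and best settled before outcome data are seen.

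- In G2, define the baseline PSWQ as the telephone reading.
- Pre-specify the screening PSWQ as a second fixed covariate in the worry model at 6 months (Aim 1) and 9 months (Aim 3). Enter it separately and do not average the two readings: the screening score is taken in person and truncated at 50, and J2 gives the instrument two names.
- List the screening PSWQ among the PROC MI variables.
- Do the same in the PHQ-9 model where a screening PHQ-9 is collected, and reconcile F2, which includes it at screening, with J2, which does not.
- State in J2 and F2 which version of the PSWQ is used on each occasion.

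The cost is SAP wording and one degree of freedom per model. No new visit, measure or data are needed, and the sample size does not change.

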## Section D: Purpose and Objectives

The overall goals of the proposed research study are to: (1) examine quantitative outcomes in a well-conducted randomized clinical trial (RCT) of CL, relative to Enhanced Community Care (ECC), an information and referral intervention that represents care in a real-world community-service environment, and (2) evaluate implementation feasibility, which includes training community providers; examining program reach, engagement, acceptability, and barriers-facilitators; and preparing practical tools for replicating the program.

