#### Exclusion Criteria:

Potential participants will be excluded only for conditions that threaten their and other's safety or those that preclude participation in the study. The exclusion criteria include 1) severe depression as indicated by a score of 20 or greater on the PHQ-9, 2) active suicidal intent, 3) psychosis, 4) bipolar disorder, 5) substance abuse within the last month, and 6) cognitive impairment indicated by 3 or fewer score on a six-item screener administered during initial assessment.

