**Specific Aim 3.** Examine the maintenance of outcomes in CL and ECC. Analyses for all primary and secondary outcomes will be repeated to examine treatment differences in outcomes at 9 months. All procedures will be as previously described.

**Analysis of Implementation Potential.** Differences in satisfaction between CL and ECC at 6 and 9 months will be examined with either an independent samples t-test or ANCOVA (if covariates are warranted). Descriptive data that address reach, participant initiation and engagement, and treatment fidelity will be reviewed by the CLC. CLC input will be used to modify the model of care if needed and to develop implementation strategies. Participant representativeness (vs. excluded participants and partner caseloads) will be examined with chi-square tests (ordinal variables) and independent sample t-tests (interval variables).

Qualitative data will be analyzed with framework analysis, whereby themes generating from both a priori issues and data are identified. Digital recordings of each qualitative interview will be transcribed verbatim into text. Transcripts will be imported into Atlas.ti to facilitate storing, management, and visualization. First, we will check transcripts for accuracy. Then, all data will be analyzed, and contact summary sheets completed after each interview, to establish a thematic framework. Raters will compare coding across transcripts and discuss/reconcile dissimilar coding. From the categories, themes within and across groups will be identified. Data analysis will identify recurring and important themes regarding acceptability, facilitators, and barriers. Descriptive statistics will characterize demographic data.

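### Representativeness is assessed by significance tests alone, with chi-square for ordinal variables and no allowance for overlap with partner caseloads, so a non-significant result is weak evidence of likeness (minor)

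*Combined protocol and SAP*

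**What the plan says.** The second overall goal in Section D is implementation feasibility, which includes "examining program reach, engagement, acceptability, and barriers-facilitators". The paragraph on implementation potential in G2 has one sentence on representativeness: "Participant representativeness (vs. excluded participants and partner caseloads) will be examined with chi-square tests (ordinal variables) and independent sample t-tests (interval variables". It gives no effect size, interval, margin or significance level for these tests, names no test for nominal variables, and does not mention people who are both participants and partner clients.

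Reach is handled in a different sentence of the same paragraph: "Descriptive data that address reach, participant initiation and engagement, and treatment fidelity will be reviewed by the CLC".

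On where participants come from, F2 says: "Recruitment will be conducted via community outreach activities and referrals from partner social service and faith-based organizations". On who is excluded, the exclusion criteria say: "Potential participants will be excluded only for conditions that threaten their and other's safety or those that preclude participation in the study". They include a PHQ-9 of 20 or more and a score of 3 or fewer on the cognitive screener. Entry also requires "significant worry as shown by a score of 50 or greater on the Penn State Worry Questionnaire (PSWQ").

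Data for the comparison begin at consent: "Participants who provide written consent will complete a demographic information form", together with the PSWQ, the PHQ-9 and the cognitive screener. Of the answers given earlier, on the interest handout, F2 says: "Any responses to these screening questions will not be used as study data".

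**The concern.** Representativeness is a claim of likeness, and a test of difference cannot establish likeness unless it would probably have found a difference that matters. Three features of the plan lower that probability.

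- The sample is modest and no estimate or interval accompanies the p-value.
- Chi-square spreads its power over every pattern of difference between categories. For an ordinal variable the pattern of interest is a shift in one direction.
- If referred participants are counted in the caseload they are compared with, the observed difference shrinks and the assumed standard error is too large.

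The excluded-participant contrast has a separate difficulty. On PSWQ and PHQ-9 the two groups are separated by the eligibility cut-offs, so a significant result there largely restates the criteria.

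At stake is how a secondary implementation result is read, in a trial motivated by under-representation of minority and low-income older adults.

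**Working it through.** **The plan's own figures (G1).** A two-sample t-test with 64 per group at d = 0.50, two-sided 0.05, has power 0.801, matching the stated 80%. Attrition: 128/0.85 = 150.6, against 150 stated. Enrolment: 150/0.50 = 300. The excluded group is therefore about 300 − 150 = 150. It would be larger if exclusion exceeds 50%, and smaller if some of the 150 withdraw rather than being excluded.

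**Step 1: participants against excluded people.** Noncentrality = d × √(150/2) = 8.66d, with two-sided 0.05 assumed because G2 gives no level here.

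- d = 0.2: noncentrality 1.73, power 0.408.
- d = 0.3: noncentrality 2.60, power 0.736.
- 80% power is reached only at d = 0.32.

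An observed difference of zero would carry a 95% interval of about ±1.96 × √(2/150) = ±0.23 SD.

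**Step 2: chi-square on ordered categories.** Simulation of 150 against 150, equiprobable categories, latent normal shift of 0.3 SD, 3,000 runs per row. The Monte Carlo standard error is at most √(0.25/3000) = 0.9 points.

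| Levels | Chi-square power | Mann-Whitney power | Loss (points) |
|---|---|---|---|
| 3 | 52% | 62% | 10 |
| 4 | 50% | 66% | 17 |
| 5 | 47% | 67% | 20 |
| 6 | 45% | 69% | 24 |

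Losses are taken from the unrounded powers. With no shift, both tests reject about 5% of the time, so chi-square is valid but inefficient. An analytic check agrees: a noncentrality of 7.85 gives 80% power on 1 df (trend) and 60% on 4 df (five-level chi-square).

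**Step 3: overlap with the caseload.** Caseload size N and the number of participants inside it are not in the documents; all values here are assumptions. Take all n = 150 inside the caseload, SD 1, and a true difference D = 0.3 between participants and the other clients.

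- Expected observed difference = (1 − n/N) × D.
- Variance assumed by the independent-samples test = 1/n + 1/N.
- True variance = 1/n − 1/N, because the participants contribute to both means.

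For N = 300, the difference is 0.5 × 0.3 = 0.15, the assumed SE is √(1/150 + 1/300) = 0.100 and the true SE is √(1/150 − 1/300) = 0.0577. The observed difference must exceed 1.96 × 0.100 = 0.196. Under no difference this happens with probability 0.0007. Under D = 0.3, (0.196 − 0.15)/0.0577 = 0.80, giving power of 21%.

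| N | Participants as share of caseload | Actual type I error | Power, overlap ignored | Power, participants removed |
|---|---|---|---|---|
| 300 | 50% | 0.0007 | 21% | 74% |
| 500 | 30% | 0.008 | 66% | 87% |
| 1,000 | 15% | 0.023 | 87% | 92% |
| 3,000 | 5% | 0.039 | 94% | 95% |
| 10,000 | 1.5% | 0.047 | 95% | 95% |

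If only 75 participants are partner clients and only they are compared, power is 39% against 61% at N = 300, and 65% against 71% at N = 1,000.

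**The case against.** **The wrong comparison group.** A reader might infer that representativeness is judged against the wrong people. The documents do not support this. The sentence names two comparators, and partner caseloads are a relevant, if imperfect, reference. The excluded group is also useful on demographics: G1 expects at least half of those enrolled to be excluded, and whether the criteria screen out particular groups is a fair question.

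**A different comparator.** A reader might also want participants compared with people who passed screening but were not randomised. Under F2, people who pass the screen go on to the SCID, and those who meet all criteria complete baseline and are randomised. The remainder are therefore largely people excluded later, plus withdrawals. People who decline before consent provide no study data.

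**A false reach result.** Reach is reviewed descriptively and is not the output of these tests. Nothing in G2 says a non-significant test will be taken as proof of representativeness. On PSWQ and PHQ-9 the tendency is the opposite, towards looking unrepresentative.

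**Overlap.** It is inferred from the referral route and its size is unknown. It cannot affect the excluded-participant contrast. If the target is the whole caseload rather than its non-participants, the smaller difference is the intended quantity and only the variance is wrong. These points stand and limit the claim to a range.

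**Chi-square.** The word ordinal may be loose wording for categorical, and G2 elsewhere allows Mann-Whitney and other methods where suitable. That clause is general and tied to the specific-aim analyses, whereas the representativeness sentence assigns chi-square to ordinal variables. If categorical was meant, the sentence still needs correcting.

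**Conclusion.** The point holds as a minor one. The plan relies on significance tests that have 41% power at 0.2 SD and 74% at 0.3 SD against about 150 excluded people, and loses a further 10 to 24 points on ordinal variables at 0.3 SD under the simulated conditions (3 to 6 equiprobable levels). Overlap with caseloads makes the second comparison conservative by an amount the documents do not allow anyone to fix: severe if participants are 30-50% of the caseload, negligible below about 5%. A non-significant result should therefore not be taken as showing likeness.

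The included-versus-excluded contrast on PSWQ and PHQ-9 reflects the eligibility rules and supports description only; the demographic contrast keeps its value. The figures assume two-sided 0.05 and 150 per group. The treatment comparisons in Aims 1-3 do not depend on any of this.

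**What to change.** Rewrite the representativeness sentence in G2 to say:

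1. For both comparators, report standardised differences with 95% confidence intervals, and base the interpretation on these rather than on p-values.
2. Use a Mann-Whitney or trend test for ordinal variables, chi-square for nominal variables, and t-tests for interval variables.
3. Tabulate PSWQ and PHQ-9 for included and excluded people without tests. Keep the demographic comparison, presented as showing whom the criteria screen out.
4. Where partners can supply counts, compare with caseload non-participants. Otherwise keep the whole caseload and use a variance that allows for the overlap. With k of n participants inside a caseload of N and a common SD, the variance is SD² × (1/n + 1/N − 2k/(nN)), which reduces to the 1/n − 1/N used above when k = n.

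The cost is slightly more tabulation and a request to partners for adjusted totals. Section K bars sending PHI outside the VA. Aggregate partner totals would respect that if the study team subtracts its own participants' values, but the team must know which participants are partner clients, including those who came through outreach. Where that cannot be established, give results over a stated range of overlap.
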